#### Hypothesis/Decision Criteria:

No specific hypotheses or pass/fail criteria have been set. The analysis will be descriptive and no statistical hypothesis tests are planned.

#### Endpoint Definition/Parameters to Be Estimated:

This endpoint is defined using variables on the AE, procedure and core lab echo CRFs.

Device success is measured at discharge, 30 days and at all later post-procedure intervals. All of the following must be present:

- Absence of procedural mortality or stroke (free from death and stroke within 30 days of procedure, AE CRF); and
- Proper placement and positioning of the device (TMVR implanted is "Yes", procedure CRF); and
- Freedom from unplanned surgical or interventional procedures related to the device or access procedure (Conversion to open MV replacement is "No" and Other repair surgery is "No", procedure CRF); and
- Continued intended safety and performance of the device, including
  - o No evidence of structural or functional failure (free from AEs for device malfunction for structural or functional failures, and free from explant and MV reinterventions, AE CRF)
    - Delivery failure (i.e., technical failure)
    - Structural failure
    - Functional failure
  - o No specific device-related technical failure issues and complications (core lab echo, AE, procedure CRF)
    - Paravalvular leak (core lab echo, AE CRF)
      - Major/Minor: Having a major paravalvular leak is considered as having a device failure.
    - Coronary vessel compression or obstruction (defined using CEC code, AE CRF)
      - Major/Minor: Having a major coronary vessel compression or obstruction is considered as having a device failure.
      - Symptomatic/Not symptomatic: Having a symptomatic coronary vessel compression or obstruction is considered as having a device failure.

- Requiring treatment/Not requiring treatment: Having a coronary vessel compression or obstruction requiring treatment is considered as having a device failure.
- Transient/Persistent: Having a persistent coronary vessel compression or obstruction is considered as having a device failure.
- Pericardial effusion (defined using CEC code, AE CRF)
  - Major/Minor: Having a major pericardial effusion is considered as having a device failure.
- Conversion to open mitral valve surgery during a transcatheter procedure (Conversion to open MV replacement is "No", procedure CRF)
- Device malpositioning (defined using CEC code, AE CRF)
- Device detachment (defined using CEC code, AE CRF)
  - Partial/Complete: Having a complete device detachment is considered as having a device failure.
- Device fracture (defined using CEC code, AE CRF)
  - Major/Minor: Having a major device fracture is considered as having a device failure.
- Damage to the native mitral valve apparatus (defined using CEC code, AE CRF)
- Interaction with non-mitral valve intracardiac structures (defined using CEC code, AE CRF)
- Device thrombosis (defined using CEC code, AE CRF)
  - Major/Minor: Having a major device thrombosis is considered as having a device failure.
- Endocarditis (defined using CEC code, AE CRF)
- Haemolysis (defined using CEC code, AE CRF)

- Reduction of MR to either optimal (post-procedure MR reduced to 0+ to trace, with no more than 1+ paravalvular MR) or acceptable (post-procedure MR reduced by at least 1 grade from baseline and to 1+ to 2+ with no more than

1+ paravalvular MR) levels without significant mitral stenosis (i.e., post-procedure EOA is  $\geq 1.5 \text{ cm}^2$  with a transmtral gradient  $< 5 \text{ mmHg}$ ) and with no greater than mild (1+) paravalvular MR (and without associated hemolysis) (core lab echo CRF)

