# The Early Feasibility Study of the Intrepid™ TMVR Transseptal System Clinical Investigation Plan

Version 4.0

Page 17 of 102

Medtronic

- No significant MV stenosis
- LV outflow tract (LVOT) patency
- Improvement in LVEF
- Improvement in cardiac output/cardiac index
- Reduction in LV end-systolic and end-diastolic dimensions
- Presence of intra-atrial shunt with clinically significant pressure gradient requiring closure device
- Change in NYHA Class from baseline through 5 years
- Change in 6MWT from baseline through 5 years
- Change in QoL from baseline through 5 years
- Procedural times (e.g., deployment time, access duration, rapid pacing duration)
- Re-hospitalizations for heart failure
- MVARC defined outcomes of: (see Appendix 17.1 for specific definitions)
  - Technical success upon exit from operating room
  - Device success at 30 days and 1 year
  - Procedural success at 30 days
  - Individual subject success at 1 year

*Medtronic Business Restricted*

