## **Appendix B: Participant Information and Consent Form**

## **Appendix C: Instructions for Use**

## Appendix D: Endpoint Definitions

Analysis of study results will include the following additional MVARC defined exploratory endpoints:

**Technical Success** (measures at exit from catheterization laboratory)

All of the following must be present:

- I. Absence of procedural mortality; and
- II. Successful access, delivery, and retrieval of the device delivery system; and
- III. Successful deployment and correct positioning of the first intended device; and
- IV. Freedom from emergency surgery or reintervention related to the device or access procedure

**Device Success** (measured at 30 days and at all later post-procedural intervals):

All of the following must be present:

- I. Absence of procedural mortality or stroke; and
- II. Proper placement and positioning of the device; and
- III. Freedom from unplanned surgical or interventional procedures related to the device or access procedure; and
- IV. Continued intended safety and performance of the device, including:
  - a. No evidence of structural or functional failure
  - b. No specific device-related technical failure issues and complications
  - c. Reduction of MR to either optimal or acceptable levels without significant mitral stenosis (i.e., post-procedure EROA is 1.5 cm^2 with a transmural gradient <5 mm Hg), and with no greater than mild (1+) paravalvular MR (and without associated hemolysis)

**Procedural Success** (measured at 30 days)

All of the following must be present:

- I. Device success (either optimal or acceptable), and
- II. Absence of major device or procedure related serious adverse event, including:
  - a. Death
  - b. Stroke
  - c. Life-threatening bleeding (MVARC scale)
  - d. Major vascular complications
  - e. Major cardiac structural complications
  - f. Stage 2 or 3 acute kidney injury (includes new dialysis)
  - g. Myocardial infarction or coronary ischemia requiring PCI or CABG
  - h. Severe hypotension, heart failure, or respiratory failure requiring intravenous pressors or invasive or mechanical heart failure treatments such as ultrafiltration or hemodynamic assist devices, including intra-aortic balloon pumps or left ventricular or biventricular assist devices, or prolonged intubation for 48 h
  - i. Any valve-related dysfunction, migration, thrombosis, or other complication requiring surgery or repeat intervention

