### Analysis Method:

The proportion of subjects with device success will be presented with its associated 95% exact confidence interval at discharge, 30 days and at all later post-procedure intervals. The numerator will include subjects with success in all components of this endpoint. The denominator will include subjects who have success or at least one failure component present.

The proportion of subjects with success for each component of this endpoint will also be presented at discharge, 30 days and at all later post-procedure intervals; the numerator will include subjects with success, and the denominator will include subjects with non-missing data.

- MVARC defined procedural success

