## 7.12 Changes to Planned Analysis

The planned analyses in this SAP are aligned with the planned analyses noted in CIP-1403. Any change to the planned analyses made prior to performing the analyses will be documented in a protocol revision prior to performing the analyses. Any change to the planned analyses made after performing the analyses will be documented in the clinical study report along with a reason for the change.

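### SAP 7.9.3 adds discharge as a device-success time point but keeps a 30-day death/stroke window there, so the discharge rate, read literally, counts events after discharge

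*Combined protocol and SAP*

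**What the plan says.** The SAP for the Pilot Study (CIP-1403), section 7.9.3, MVARC defined device success, sets the time points: "Device success is measured at discharge, 30 days and at all later post-procedure intervals". Its analysis method plans the proportion with a "95% exact confidence interval at discharge, 30 days and at all later post-procedure intervals", and the success proportion for each component at the same time points. Discharge is therefore a planned output.

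The first component is given one operational rule for all time points: "free from death and stroke within 30 days of procedure, AE CRF". Nothing in the definition or the analysis method shortens it at discharge. For the composite, "The denominator will include subjects who have success or at least one failure component present".

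CIP-1403 Appendix D has device success "measured at 30 days and at all later post-procedural intervals", without discharge. Its corresponding component, "Absence of procedural mortality or stroke; and", carries no day window; the 30 days come from the SAP. SAP section 7.12 states: "The planned analyses in this SAP are aligned with the planned analyses noted in CIP-1403".

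The transseptal early feasibility CIP in the same file lists "Device success at 30 days and 1 year". It is not the plan that this SAP serves, so it is context only.

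**The concern.** A rate labelled as measured at discharge should describe what was known at discharge. Here one component runs to day 30 whatever the time point. For anyone discharged before day 30, a later death or stroke would change the discharge result.

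Two outputs are touched. The discharge composite is lowered by events that had not yet happened. The death/stroke component rate at discharge repeats the day-30 information and does not describe the hospital stay. Two programmers could also produce different discharge rates from the same data, one following the stated window and the other stopping at discharge, because the SAP does not say which applies.

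**Working it through.** The plan states no figure to reproduce: the sample size is not statistically derived and no success criterion is set. The check is first textual, then a simple illustration of size.

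**Step 1: window against time point**

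- Technical success (SAP 7.9.3) is measured at exit from the catheterization laboratory, and procedural mortality there means death on day 0. The window fits the time point.
- Device success at 30 days and later uses death or stroke within 30 days. The window fits the earliest time point in Appendix D.
- Device success at discharge uses the same 30-day window. It does not fit for any subject discharged before day 30.
- The mismatch also runs the other way. In a subject still in hospital after day 30, a death or stroke between day 30 and discharge would not count in this component at discharge.

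**Step 2: size per event**

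Inputs: up to 95 treated subjects (SAP section 6) and a first interim analysis at 50 subjects (SAP section 7.8). Let D be the composite denominator, S the successes when only events through discharge count, and k the otherwise successful subjects who die or have a stroke after discharge but by day 30.

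Rate under the literal rule = (S − k)/D, so the shift is k/D. Per event this is 1/95 = 1.05 points, or 1/50 = 2.0 points. It does not depend on S.

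The table assumes S/D = 80% and several values of k. Neither comes from the documents. Intervals are exact (Clopper-Pearson) 95% intervals.

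| k | D = 95 | D = 50 |
|---|---|---|
| 0 | 76/95 = 80.0% (70.5–87.5) | 40/50 = 80.0% (66.3–90.0) |
| 1 | 75/95 = 78.9% (69.4–86.6) | 39/50 = 78.0% (64.0–88.5) |
| 3 | 73/95 = 76.8% (67.1–84.9) | 37/50 = 74.0% (59.7–85.4) |
| 5 | 71/95 = 74.7% (64.8–83.1) | 35/50 = 70.0% (55.4–82.1) |
| 8 | 68/95 = 71.6% (61.4–80.4) | 32/50 = 64.0% (49.2–77.1) |

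A subject with a late event who already fails another component at discharge shifts nothing. The composite is strict (it requires, for example, an orifice area of at least 1.5 cm² and a gradient below 5 mmHg), so k may be well below the number of late events.

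**Step 3: the denominator rule**

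A subject without a usable discharge echo and with no failed component is left out of the composite denominator. If that subject dies on day 20, the literal rule brings the subject in as a failure at discharge, while a similar survivor stays out. The rate moves from S/D to S/(D + 1): for example, 76/94 = 80.9% becomes 76/95 = 80.0%, a drop of about 0.85 points.

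**The case against.** The strongest reply is that the time point itself supplies the cut-off. Endocarditis, thrombosis, fracture, haemolysis and reintervention carry no window in the same definition. They make sense only if counted up to the stated time point, since otherwise a fracture in year 4 would be a failure at discharge. On that reading, the 30 days are an upper limit that keeps later deaths out of the procedural item at 1 to 5 years. This is a fair reading, and it shows that the text is ambiguous. It works for the components without a window. It works less well for the one component that states its own window, with nothing to say that an earlier time point overrides it.

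The window may also be deliberate. The MVARC classification reproduced in the transseptal CIP (17.1.32 and 17.1.34) treats death and stroke within 30 days as periprocedural, and CIP-1403 and the SAP also draw on MVARC. That justifies the window at 30 days but does not make the result a status at discharge.

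Two stronger inferences are not supported:

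- **That discharge is undefined in the CIP.** CIP-1403 section 4.5 and its Appendix A schedule a discharge assessment with echo, ECG, laboratory tests and adverse-event review. What is missing is device success at that visit.
- **That change from discharge to 30 days cannot be read.** The SAP reports every component separately at each time point, so the echo components stay readable. SAP section 7.10 adds a listing of deaths, safety summaries by time point and Kaplan-Meier estimates, and section 7.2 provides case summaries for every subject. What is lost is the contribution of death and stroke to any difference between the two composite rates. The SAP specifies no formal comparison of the two.

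**Conclusion.** The point holds as a small, specific defect in one planned output. The SAP reports device success at a time point for which CIP-1403 does not define it, and its explicit 30-day death/stroke window, followed literally, brings post-discharge events into the discharge composite and into that component's rate.

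The size is 1.05 points per qualifying event at a denominator of 95 and 2.0 points at 50. This rests on three assumptions: the literal reading is the one programmed, the subject was discharged before day 30, and the subject was otherwise a success. A smaller evaluable denominator makes each event weigh more. A reader might take a total such as 3/95 = 3.2 points as an estimate of the bias. The documents do not support that: no event count is given, and for three events at that denominator 3.2 points is reached only if all three subjects were otherwise successful.

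The 30-day and later device-success rates are not affected. The endpoint is exploratory and descriptive, with no pass/fail criterion, so no study conclusion turns on this.

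**What to change.** In SAP 7.9.3, device success:

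- State that at the discharge time point death, stroke and the other event components are counted only through the discharge date, and that a death before discharge is a failure.
- Keep the 30-day death/stroke window for 30 days and later.
- Label discharge as a SAP addition to CIP-1403, and record the change by the route in SAP section 7.12: a protocol revision if made before the analysis, the clinical study report if after.

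The alternative is to remove discharge from the definition and the analysis method, which restores agreement with Appendix D. That gives up an early composite. The SAP version history says the MVARC criteria were added at FDA request, and the documents do not show whether that request covered discharge, so this should be checked before dropping it.

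The cost is a small text and programming edit on an exploratory endpoint. No new data are needed beyond the discharge and event dates.

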- Other systemic effects or symptoms (e.g., abnormal lab values, electrolyte imbalance, fever, hyperthermia, hypotension, hypertension, syncope, nausea, vomiting, edema, deep vein thrombosis, pleural effusion, lymphatic complications, urinary tract infection, multi-system organ failure, gastrointestinal bleeding, ischemia or infarction)
- Valve implant dysfunction (e.g., fracture, bending, under-expansion, suture breaks, calcification, pannus, thrombus, inflammation, stenosis, leaflet wear, tear, prolapse, retraction, poor valve coaptation, leaks, regurgitation, mal-sizing [prosthesis-patient mismatch])

The risks of the investigational TMVR procedure are similar to the surgical risks listed above; however some may be increased with the TMVR procedure or implant. For example, the risks of cardiac damage may be increased by the TMVR delivery, and the risk of valve implant dysfunction (as compared to surgical replacement valves) has not yet been established.

In addition to the risks listed above, the potential risks associated with the TMVR procedure and the Intrepid TMVR System may include, but are not limited to, the following risks:

- Valve implant detachment, migration, malposition, and/or incorrect sizing
- Reduced ventricular function due to apical incision and sheath insertion
- Ventricular insertion site complications (e.g., bleeding, rupture, septal perforation, aneurysm or pseudoaneurysm)
- Injury to mitral valve apparatus complicating or preventing later surgical repair/replacement
- Left ventricular outflow tract (LVOT) obstruction
- Emergent surgical or transcatheter intervention (for example, coronary artery bypass, heart valve replacement or repair, transcatheter valve explant, percutaneous coronary intervention [PCI], balloon valvuloplasty, transcatheter valve or component retrieval)
- Failure to deliver the bioprosthetic to the intended site
- Failure to retrieve the system components
- Delivery system component(s) embolization
- Delivery system thrombosis
- Prolonged cardiopulmonary bypass
- Prolonged ventilation, anesthesia, and/or procedure time
- Radiation skin burn or tissue reaction

The likelihood of these risks is unknown, as this is the initial introduction of the investigational TMVR system into a human population. However, bench-top testing and animal studies have

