## Endpoint Definition/Parameters to Be Estimated:

This endpoint is defined using variables on the AE and procedure CRFs.

Technical success is measured at exit from the catheterization laboratory and all of the following must be present:

- Absence of procedural mortality (free from death on day 0, which is day of procedure, AE CRF); and
- Successful access, delivery, and retrieval of the delivery system (same definition as secondary endpoint, procedure CRF); and
- Successful deployment and correct position of the first intended device (TMVR implant is "Yes", no additional devices opened or used, TMVR device malfunction is "No", and TMVR device failure is "No", procedure CRF); and
- Freedom from emergency surgery or reintervention related to the device or access procedure (Conversion to open MV replacement is "No" and Other repair surgery is "No", procedure CRF).

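### Pilot SAP 7.9.3 scores the unplanned-procedures component of device success from the index-procedure form alone, so later access-related procedures, and device-related ones outside the listed failures, are not counted

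*Combined protocol and SAP*

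**What the plan says.** The SAP in this file belongs to the trans-apical pilot (CIP-1403), not to the transseptal study whose protocol is bound with it. This point concerns the pilot.

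- **Timing.** SAP 7.9.3: "Device success is measured at discharge, 30 days and at all later post-procedure intervals". All components must be met.
- **The component at issue (third of four).** SAP 7.9.3: "Freedom from unplanned surgical or interventional procedures related to the device or access procedure (Conversion to open MV replacement is" no, together with "Other repair surgery is 'No', procedure CRF". No other data source is named for it.
- **The counterpart in technical success.** This endpoint is measured on leaving the catheterization laboratory: "Freedom from emergency surgery or reintervention related to the device or access procedure (Conversion to open MV replacement is" no, with the same second item from the same form.
- **The protocol definition.** Pilot CIP Appendix D, Device Success III: "Freedom from unplanned surgical or interventional procedures related to the device or access procedure; and". It is measured at 30 days and at all later intervals, with no restriction to the index procedure.
- **The fourth component in the SAP.** It draws on the AE CRF and core-lab echo as well as the procedure CRF. It requires subjects to be "free from explant and MV reinterventions, AE CRF", and it fails them for a list of complications, for example: "Having a coronary vessel compression or obstruction requiring treatment is considered as having a device failure".
- **Reporting.** The device-success analysis method gives the composite and each component separately, at discharge, 30 days and every later interval.

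**The concern.** A component meant to be followed from 30 days to 5 years is scored with the fields, and so with the time horizon, of an endpoint that closes when the patient leaves the room. Appendix D words the two endpoints differently: emergency surgery or reintervention for technical success, any unplanned surgical or interventional procedure for device success. The SAP gives both the same rule. As labelled, the two fields also describe surgery, so the interventional half of the component has no evident field.

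This does not read as a declared choice. Where the SAP drops an MVARC criterion (return to the pre-procedural setting, in individual subject success), it says so and gives a reason. Here it says nothing, and SAP 7.12 states that the analyses are aligned with CIP-1403.

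Later access-related procedures are plausible in a trans-apical study. Pilot CIP 5.2 lists among its risks: "Ventricular insertion site complications (e.g., bleeding, rupture, septal perforation, aneurysm or pseudoaneurysm". The MVARC criteria entered the SAP at FDA's request (Version History, 2.0), and SAP section 5 says results will be read against historical literature. A proportion labelled as freedom from unplanned procedures should therefore measure that at the time stated.

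**Working it through.** The plan gives no device-success figure, event rate or hypothesis, so there is nothing to reproduce. The check is a comparison of texts, followed by simple arithmetic.

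**Step 1. What the fields can record.** Conversion to open mitral valve replacement and other repair surgery sit on the procedure CRF. The CRFs are not in the documents. I assume that this form records only the index procedure, as its items suggest. On that assumption a subject's result on the third component is fixed at the end of the index procedure and is the same at 30 days and at 5 years. The component's own proportion cannot register any later procedure, not even an explant.

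**Step 2. Follow later events through the composite.**

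| Later event | Third component | Fourth component | Device success |
|---|---|---|---|
| Explant or mitral valve reintervention | Pass | Fail (AE CRF) | Fails |
| Coronary obstruction needing treatment | Pass | Fail | Fails |
| Major pericardial effusion, major paravalvular leak, malpositioning, complete detachment, major fracture, major thrombosis, endocarditis, haemolysis | Pass | Fail | Fails |
| Re-exploration or repair at the apical or thoracotomy access site | Pass | Fails only if coded as a listed complication, such as major pericardial effusion or interaction with non-mitral intracardiac structures | Depends on coding |
| Vascular access repair | Pass | No matching item | Not failed |
| Device-related procedure with no explant, mitral valve reintervention or listed complication | Pass | No matching item | Not failed |

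The gap in the composite is the last two rows, and the fourth row when no listed code applies.

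**Step 3. Direction.** The SAP denominator is subjects with full success plus subjects with at least one failure. Let *S* be scored successes, *F* scored failures, *m* the scored successes who had a missed procedure, and *k* the subjects with a missed procedure who are now outside the denominator because of missing data.

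- As written: S / (S + F)
- Counting the missed procedures: (S − m) / (S + F + k)

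With *m* and *k* at zero or above, the second cannot exceed the first. The bias can only be upward.

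**Step 4. Size per subject.** With *k* = 0, each missed subject shifts the rate by 1 / (S + F):

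- 95 evaluable (maximum treated, SAP section 6): 1/95 = 1.05 percentage points
- 75 evaluable (second interim count, SAP 7.8): 1/75 = 1.33 points
- 50 evaluable (first interim count, SAP 7.8): 1/50 = 2.00 points

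Illustration only, assuming 95 evaluable and 76 scored as successes, with exact 95% intervals:

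| m | Rate | 95% CI | Shift (points) |
|---|---|---|---|
| 0 | 76/95 = 80.0% | 70.5 to 87.5 | 0 |
| 1 | 75/95 = 78.9% | 69.4 to 86.6 | 1.1 |
| 3 | 73/95 = 76.8% | 67.1 to 84.9 | 3.2 |
| 5 | 71/95 = 74.7% | 64.8 to 83.1 | 5.3 |
| 10 | 66/95 = 69.5% | 59.2 to 78.5 | 10.5 |

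**Step 5. Endpoints built on device success.** Individual subject success at 1 year requires device success and adds only rehospitalizations and reinterventions for the underlying condition, so an access repair still goes uncounted. Procedural success at 30 days is partly protected. It separately lists life-threatening bleeding, major vascular and cardiac structural complications, and valve-related complications needing surgery or repeat intervention.

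**The case against.** The strongest reply is that the composite already works for most later procedures. Every component must be met, and the fourth takes explants, mitral valve reinterventions and a long list of device complications from follow-up data. Most device-related reasons for a later procedure are therefore failures already, and an apical bleed or pseudoaneurysm might be coded as one of the listed complications. This stands. A reader might infer that procedures after room exit never count in device success; the fourth component shows that they often do. It does not close the gap for vascular access repair, for access-site procedures without a listed code, or for the third component's own reported proportion.

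Second, the events are visible elsewhere. A return to theatre would normally be a serious adverse event under pilot CIP 6.1. If related to the device or procedure, it counts in the primary safety endpoint through 30 days (SAP 7.9.1), and it appears in the SAP 7.10 listing and in the case summaries. Device success is exploratory, is listed only in the US and France CIPs, and has no pass/fail criterion. All of this lowers the stakes, but none of it makes the component measure what its label says.

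Third, the procedure CRF is not available, so its scope is inferred. That is a fair limit on confidence.

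**Conclusion.** The mismatch holds in a limited form. The third component of device success is scored with the rule for technical success, although its wording, its assessment times and Appendix D all extend beyond the index procedure. The component's reported proportion is blind to every later procedure. The composite is blind only to later access-related procedures, and to device-related ones that involve no explant, mitral valve reintervention or listed complication. Device success can only be overstated as a result. Individual subject success at 1 year inherits the bias, and procedural success is partly protected.

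The size is unknown. A reader might infer from the illustration an overstatement of several points, but the documents give no rate of such procedures and no basis for choosing one. All they support is the step per missed subject: about 1.05 points if all 95 are evaluable, and more where the denominator is smaller, since it varies by visit.

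The conclusion rests on the procedure CRF covering only the index procedure. Because the endpoint is exploratory and the events are reported elsewhere, this should be corrected but does not threaten the study's main safety reporting.

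**What to change.** In SAP 7.9.3, device success, score the component as met when both conditions hold:

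1. On the procedure CRF, conversion to open mitral valve replacement and other repair surgery are both answered no.
2. On the AE CRF, there is no CEC-adjudicated unplanned surgical or percutaneous procedure related to the device or to the TMVR/access procedure, from the end of the index procedure through the time point assessed.

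Keep the procedure-CRF-only rule for technical success, where it fits.

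The cost is one SAP sentence and minor reprogramming. The CEC already adjudicates all serious adverse events (SAP 5.3 and 7.10). One step may be new: SAP 7.9.1 shows relatedness recorded to the device/procedure, with no separate access field, so the CEC may have to attribute events to access. The reported success rate may also fall slightly.
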